#### III. Intervention

- a. Low dose Intranasal insulin 10 international units BID (LDINI)
- b. High dose Intranasal insulin 20 international units BID (HDINI)
- c. Placebo (PLAC)
- IV. Outcomes:
  - a. Primary outcome
    - i. Change from baseline in cognitive function as assessed by the Symbol Digit Modalities Test (SDMT) using raw scores
  - b. Secondary outcomes
    - i. Adverse events
      - Adverse events are defined as occurrence or worsening of an undesirable or unintended sign, symptom, or abnormal laboratory test potentially associated with INI. Adverse events for this study will consider: outcomes for which ≥5% experienced. Adverse events will be characterized overall and stratified by treatment arm).
      - 2. Evaluation of glucose levels (from finger-stick) for first 15 participants following first dose of medication.
      - 3. Number of adverse events comparing any INI versus placebo or HDINI versus LDINI versus placebo (e.g., two level any exposure to INI versus three level incorporating dosages).
    - ii. Change from baseline cognitive function in the tests listed below. Cognitive outcomes will be assessed as raw scores
      - 1. Change from baseline cognitive function in Controlled Oral Word Association Test (COWAT) assessing fluency (adjusted for form type)
        - a. Number of words produced in one minute for each of the three letters (raw score)
        - b. Number of words produced in one minute for each of the three letters (adjusted score)
      - 2. Change from baseline using Benton Judgement of Line Orientation (JLO) test assessing participant ability to match the angle and orientation in space
        - a. Total correct
      - 3. Change from baseline using PASAT-3 test assessing processing speed
        - a. Total correct
      - 4. Change from baseline using Brief Visuospatial Memory Test Revised (BVLT-R) assessing learning and memory. The following aspects from the BVLT-R will be considered.
        - a. Total recall
        - b. Delayed recall
      - 5. Change from baseline using Delis-Kaplan Executive Function System sorting (DKEFS) test for executive functioning. The following aspects from the DKEFS will be considered:
        - a. Total description score
        - b. Number of correct sorts
      - 6. Change from baseline using California Verbal Learning Test (CVLT) for learning and memory. The following aspects from the CVLT will be considered and combined into a composite outcome for CVLT using Z scores.
        - a. Long-delay free recall correct
    - iii. Change in multiple sclerosis (MS) functional composite (MSFC)
      - 1. Change in components of MSFC. These include walking speed, 9-hole peg test, and PASAT-3.
      - 2. MSFC will be considered as a Z score; MSFC component tests will be assessed as raw and Z scores.

- 3. Sustained 20% worsening from baseline MSFC that is confirmed at a subsequent visit.
  - a. This test will only be performed if at least 10 events have occurred.
- iv. Change in health-related quality of life using the functional assessment in MS (FAMS) scores
  - 1. These include the total FAMS score and components for symptoms, mobility, fatigue, emotional well-being, social well-being
  - 2. 1 SD improvement in FAMS total and component scores
- v. Change in sleep quality
  - 1. Total Pittsburgh Quality Sleep Index global score
- vi. Change in depression using Beck Depression Inventory-II
- 1. Change in total depression score

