All study visits will be scheduled for the morning to reduce variability in cognitive function related to the time of day. At baseline, fasting laboratory testing will be performed, including a hemoglobin A1c test and insulin level. All subjects will then be given breakfast prior to completing cognitive testing. For follow-up visits, all subjects will complete the MACFIMS battery after eating a usual meal (if the participant came without having eaten, breakfast will be provided to them) and prior to taking the morning dose of study treatment. Unscheduled visits will occur if any safety issue arises.

In order to ensure subjects (or their responsible caregivers) are able to use the medication as instructed, all subjects and caregivers (when relevant) will be instructed on the use of the inhaler and will be observed by a health care provider when performing their first dose administration at the time of the first visit.

Risks

Intranasal insulin

Intranasal insulin has been shown to be safe and tolerable in other populations and patient groups, but it has never been studied in people with MS. The most common side effects related to irritation of the nasal passages. Giving insulin through the nose did not result in lower circulating glucose levels in other studies, but the first 15

people in this study will be monitored for this potential risk by testing a fingerstick blood glucose level periodically for 90 minutes after the first dose of intranasal insulin (see Safety section under **Outcomes** on page 10).

Insulin, given by the more traditional subcutaneous route, has the following potential risks:

Hypoglycemia: Common symptoms of hypoglycemia include sweating, dizziness or lightheadedness, shakiness, hunger, a fast heartbeat, tingling of the hands, feet, lips or tongue, trouble concentrating, confusion, blurry vision, slurred speech, anxiety, irritability, or mood changes, or headache. Very low blood sugar can cause loss of consciousness, seizures, or temporary or permanent brain problems or death. Mild hypoglycemia can be treated by drinking or eating something sugary right away (fruit juice, sugar candies, or glucose tablets).

Hypokalemia: Hypokalemia can lead to breathing problems, low heartbeat, or death.

Allergic reaction: Common symptoms of an allergic reaction include a rash all over the body, trouble breathing, a fast heartbeat, sweating, and feeling faint.

Weight gain or swelling of the arms and legs.

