Safety/Adverse Event Monitoring An adverse event (AE) is any occurrence or worsening of an undesirable or unintended sign, symptom (or abnormal laboratory test), or disease temporally associated with the use of a medicinal product or intervention, whether or not it is considered related to the product/intervention. We will use the National Cancer Institute's Common Terminology Criteria for Adverse Events version 4.0 to report and grade all adverse events, whether or not they are related to disease progression or treatment. The relationship between an AE and the intervention will be determined by the blinded study physician and recorded on the appropriate form. The investigator will record all study adverse events in the chart and will treat participants with AEs appropriately, observing them until they resolve or stabilize. AEs will be collected from the start of the study until a participant terminates from the study; those that are unresolved at the time of termination will be followed until they resolve or up to 30 days. An adverse event is considered unexpected when its nature or severity is not consistent with the product information (e.g. protocol or the informed consent form). Serious AEs will be collected from informed consent signing until 30 days after study completion or until 30 days after a participant withdraws from the study. The following process for reporting a serious AE will ensure compliance with the International Conference on Harmonisation guidelines: the Institutional Review Board (IRB) and DSMB will be notified in two business days of a serious AE that is medication-related and unexpected, and standard reporting (15 calendar days) will occur if the event is serious, expected and medication-related, serious, expected and not medication-related, or serious, unexpected and not medicationrelated. Life-threatening events will be reported within 7 calendar days. Any pregnancy will be reported to the IRB and DSMB, and pregnancies will be followed to their conclusion. Female participants who become pregnant will stop the study intervention. The investigator will report pregnancies to the IRB within two business days. The study medication will be discontinued if an AE grade 3 or higher occurs and is at least possibly related to the medication or if the subject cannot tolerate the medication/ wants to discontinue it. Any death that is at least possibly related to the study will put the study on hold until the DSMB evaluates it.

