Aim 1. Safety data will be analyzed as they are captured in real time. Assessments will focus on AEs (including study treatment tolerability assessments, laboratory evaluations, vital signs, and physical examination). The incidence rate of AEs will be recorded by system organ class, severity, and by relationship to the study treatment. Tolerability analysis will be based on the number (%) of subjects who failed to complete the study due to adverse events. Lab values for each parameter will be summarized by shift tables. For quantitative parameters, summary statistics for actual values and change from baseline will be presented. Changes in the first 24 weeks will be compared between groups using mixed effects regression analyses to account for the longitudinal nature of the data using random subject-specific intercepts and slopes.

Aim 2. Summary statistics (mean ± standard deviation, median and interquartile range, or number and percentages) will be used to characterize the outcomes. For each cognitive outcome, to evaluate variability in the estimated means across groups, assuming that the within-group means are normally distributed, a one-way ANOVA will be conducted at the follow-up visits during the first 24 weeks. If the within-group data are strongly non-Gaussian, a Kruskal-Wallis test will be used. A mixed effects longitudinal model will also be used to test whether any differences across groups exist at the follow-up visits within the first 24 weeks. Further, models accounting for covariates of interest, including the HOMA-IR, body composition, body mass index, age, sex and depression, will be used. For within-person changes in measures at follow-up compared to baseline, paired t-tests will be used. We will also evaluate the SDMT at each study visit and other MACFIMS outcomes at week48 to establish the longevity of any therapeutic response to insulin.

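### The SAP's adverse event definition adds a relatedness condition that the protocol's does not have; read literally, it restricts the between-arm safety comparison

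*SAP*

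**What the plan says.** **Protocol.** Under Safety/Adverse Event Monitoring, an adverse event is an undesirable sign, symptom (or abnormal laboratory test) or disease that is "temporally associated with the use of a medicinal product or intervention, whether or not it is considered related to the product/intervention". CTCAE version 4.0 is used "to report and grade all adverse events, whether or not they are related to disease progression or treatment". Relatedness is recorded separately: "The relationship between an AE and the intervention will be determined by the blinded study physician and recorded on the appropriate form". In the Analytic Plan, Aim 1, it serves as one of three ways of classifying events: "The incidence rate of AEs will be recorded by system organ class, severity, and by relationship to the study treatment".

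**SAP.** Section IV.b.i, item 1, reads: "Adverse events are defined as occurrence or worsening of an undesirable or unintended sign, symptom, or abnormal laboratory test potentially associated with INI". Most of this follows the protocol's sentence, with three changes. The temporal link becomes a potential association with insulin, the clause that makes relatedness irrelevant is gone, and disease is no longer listed. The item then adds a frequency restriction: "Adverse events for this study will consider: outcomes for which ≥5% experienced". Item 3 sets the comparison: "Number of adverse events comparing any INI versus placebo or HDINI versus LDINI versus placebo". Section VIII.h.i names adverse events as an outcome but gives no method.

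**The concern.** Safety and tolerability is the protocol's primary objective, and the protocol says both are unknown in MS. In a randomised, blinded trial the contrast between arms estimates how many events the drug causes. No case-by-case causality call is needed before counting. If one is made, an event that insulin caused but the assessor attributes to MS, or to anything else, drops out of the comparison.

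The literal SAP rule has this effect, and its terms are open. It does not say how likely the association must be or who decides. It also does not say how the test applies to a placebo participant, who received no insulin. Dropping disease from the definition adds a second narrowing: a new or worsening diagnosis, as distinct from a sign or symptom, is no longer plainly included.

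**Working it through.** **1. The two definitions side by side**

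| Element | Protocol | SAP Section IV.b.i |
|---|---|---|
| Link to treatment | Temporal | Potential association with insulin |
| Relatedness | Irrelevant to inclusion | Part of the definition, read literally |
| Disease | Included | Not listed |
| Assessor of relatedness | Blinded study physician | Not named |
| Threshold of relatedness | Not needed for inclusion | Not stated |
| Use of relatedness in analysis | Classification in tables | Condition for being counted, read literally |

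The conflict follows from the text alone. SAP Sections III to IX, the part available for this review, contain no all-cause comparison that would restore the protocol's definition.

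**2. What a relatedness condition could do**

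The plan has no figure on this point to reproduce, so this step is an illustration.

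From the protocol: 35 participants per group, so n0 = 35 on placebo and n1 = 2 × 35 = 70 on either insulin dose; two-sided alpha 0.05.

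Assumed: true any-event proportions of p0 = 0.20 on placebo and p1 = 0.45 on insulin, and kept shares s of 0.8, 0.6 and 0.4. Each participant is counted as having an event or not, a simplification of the SAP's count of events. There is no drop-out, and the 5% cut is not applied.

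Power = Φ[(|p1 − p0| − 1.96 × SE0) / SE1], where SE0 = √[p̄(1 − p̄)(1/n0 + 1/n1)], p̄ is the pooled proportion, and SE1 = √[p0(1 − p0)/n0 + p1(1 − p1)/n1].

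All events counted:
- p̄ = (35 × 0.20 + 70 × 0.45)/105 = 0.367
- SE0 = √[0.367 × 0.633 × (1/35 + 1/70)] = 0.0998
- SE1 = √[0.20 × 0.80/35 + 0.45 × 0.55/70] = 0.0900
- Power = Φ[(0.25 − 1.96 × 0.0998)/0.0900] = Φ(0.605) = 0.727

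Three kinds of removal, with the same formula:

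| What is removed | Rates after removal | Excess in points (s = 0.8, 0.6, 0.4) | Power (s = 0.8, 0.6, 0.4) |
|---|---|---|---|
| Nothing | 0.20 vs 0.45 | 25 | 0.727 |
| Equal share of all events in both arms | s × p0 vs s × p1 | 20, 15, 10 | 0.572, 0.406, 0.251 |
| Only insulin-caused events | p0 vs p0 + s(p1 − p0) | 20, 15, 10 | 0.539, 0.342, 0.181 |
| Only unrelated background events | s × p0 vs s × p0 + (p1 − p0) | 25, 25, 25 | 0.758, 0.798, 0.850 |

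Other assumed rates give the same pattern. At 10% vs 30%, power is 0.648 with all events counted. At s = 0.6 it is 0.367 (equal share), 0.306 (insulin-caused only) and 0.726 (background only). At 30% vs 55% it is 0.687, and at s = 0.6 it is 0.354, 0.309 and 0.741.

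The condition can therefore hurt or help. The documents do not fix which events it would remove.

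**The case against.** **It may be loose drafting.** The SAP sentence follows the protocol's closely, and the changed phrase may be a careless rendering of the temporal link. The SAP names no relatedness category, assessor or exclusion step and does not refer to the recorded relationship field. Item 3 counts events in placebo participants, which fits poorly with a strict insulin-association rule. All this stands: a reader might infer that the comparison is certainly filtered, and the documents show only that the literal text says so. The wording still needs correcting, because an analyst who follows it would depart from the protocol.

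**Judgement is blinded.** Under the protocol a blinded physician assesses relatedness. With blinding intact, bias towards one arm by knowledge of assignment is unlikely. That stands. It does not prevent loss of events in both arms, and proportional loss shrinks the absolute excess while leaving the risk ratio unchanged (0.45/0.20 = 2.25 in every row of that scenario).

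**Is attribution unreliable in MS?** A reader might infer this from the overlap between listed hypoglycemia symptoms and MS. The protocol's list begins "Common symptoms of hypoglycemia include sweating, dizziness or lightheadedness, shakiness, hunger, a fast heartbeat, tingling of the hands, feet, lips or tongue" and goes on to poor concentration and confusion, while the Introduction names attention and processing speed among the domains that MS affects. But the list is given for subcutaneous insulin. The protocol says none of those risks was shown in published intranasal trials and gives nasal irritation as the most common effect. Neither document says that relatedness calls are unreliable. Misattribution is a possibility, not a documented fact.

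**All-cause reporting continues.** The protocol still requires all events to be graded and reported, and nothing in the SAP sections read here withdraws that. This stands too: the point is confined to the SAP's definition and the comparison built on it.

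**Conclusion.** The concern holds as a conflict of definitions. Read literally, the SAP puts a relatedness condition, with no threshold and no assessor, on the between-arm comparison that addresses the protocol's primary objective, and it omits disease. The protocol does neither.

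The stronger conclusion that the SAP makes insulin look safer than it is does not follow. Losing insulin-caused events, or an equal share of all events, shrinks the absolute excess and the power. Removing only unrelated events leaves the excess unchanged and raises power. In the illustration the range runs from 0.181 to 0.850 around an all-cause value of 0.727. It rests wholly on assumed event rates and kept shares and should be quoted in both directions or not at all.

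Collection of adverse events and expedited reporting under the protocol are unaffected. The 5% frequency cut and the SAP's listing of adverse events as a secondary outcome are separate matters and carry no weight here.

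**What to change.** 1. Replace the definition in SAP Section IV.b.i, item 1, with the protocol's all-cause definition, including disease, and state that relatedness does not decide whether an event is counted.
2. Make all-cause adverse events by arm the main comparison in item 3, and refer to it under Section VIII.h.i.
3. Show events judged related by the blinded physician in a secondary table by arm, using the relationship field that the protocol already records. State which categories of that field count as related.

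The cost is SAP wording and one extra table. No new data are needed, because the protocol already collects all events and their judged relationship.

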Intranasal Insulin for Cognition in MS is an Innovative Treatment Approach-Summary

Insulin appears to activate biologically relevant pathways within the nervous system for regulating and improving learning and memory. The direct and indirect effects of insulin on energy metabolism, oxidative stress, and modulation of inflammatory and neuronal pathways, along with the data from clinical trials in people with other neurodegenerative disorders, prove the rationale for investigating it in people with MS who suffer with cognitive impairment. As noted above, reduced levels of insulin and/or insulin activity may contribute to a number of pathological processes that may ultimately lead to long-term disability in neurodegenerative diseases. Restoring brain insulin to normal levels and increasing insulin sensitivity in the brain may provide therapeutic benefit to people with MS. Herein, we thus propose the first clinical trial in MS to determine the safety and tolerability as well as the effectiveness of intranasal insulin as a therapeutic intervention for cognitive dysfunction. Our study will investigate associated changes in putative biomarkers (see Preliminary Data below) that may corroborate clinical outcomes and provide data regarding the mechanisms by which insulin acts. These measures, along with neuropsychological testing, will be incorporated with safety data in order to accurately assess the potential utility of intranasal insulin for MS cognitive impairment.

OBJECTIVES/AIMS

Primary Objective: To evaluate the safety and tolerability of intranasal insulin in people with MS

Secondary Objectives: The main secondary objective is to evaluate if intranasal insulin improves cognition in people with MS, as assessed by the SDMT. Additional secondary objectives are to determine if intranasal insulin is associated with changes in additional components of the Minimal Assessment of Cognitive Function in MS (MACFIMS), the Multiple Sclerosis Functional Composite (MSFC) score, health-related quality of life

(Functional Assessment of Multiple Sclerosis [FAMS]), the Expanded Disability Status Scale (EDSS) score, and changes in biomarkers of oxidative stress, neuronal injury, cellular stress, and metabolism.

Aim 1. To evaluate the safety and tolerability of intranasal insulin in people with MS.

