## VII. Consort diagram

a. A consort diagram will be created with the following levels: assessed for eligibility, randomized, treatment allocation, follow-up and analytic cohort.

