#### IX. Regression models: Planned per protocol analyses

- a. For planned per protocol analyses, we will consider the following analyses for the primary outcome raw change in SDMT (or corresponding measures of processing speed)
- b. Overview of planned per-protocol analyses

- i. Adjusted analyses for additional covariates including DXA-derived body fat, bone density, lean mass, BMI, HOMA-IR
- ii. Stratified analyses by pre-shutdown and shutdown/post-shutdown.
  - 1. Pre-shutdown will be considered as all study visits occurring before March 13, 2020, shutdown will be considered from after March 13, 2020.
- iii. Analyses including excluding any screening SDMT for those missing the baseline SDMT.
- iv. Stratified analyses by key covariates of interest; these will be tested using an interaction term.
  - 1. Disability status (EDSS< median, EDSS≥median), history of depression, number of non-MS medications (<5, ≥5), MS subtype (RRMS, progressive), DMT (yes, no)
- v. Assessing predictors of drop-out/early censoring
  - 1. Baseline covariates will be used to assess whether certain characteristics were associated with follow-up time.

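### Protocol and SAP disagree on whether safety or SDMT is primary, and the SAP's adverse event wording is narrower than the protocol's, with an undefined 5% rule and no tolerability count in the visible text

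*SAP*

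**What the plan says.** **Rank of the outcomes.** The protocol (Objectives/Aims) states: "Primary Objective: To evaluate the safety and tolerability of intranasal insulin in people with MS". It calls SDMT cognition the main secondary objective. SAP IV.a gives the primary outcome as "Change from baseline in cognitive function as assessed by the Symbol Digit Modalities Test (SDMT) using raw scores" and VIII.g repeats SDMT as primary. AEs appear under secondary outcomes (IV.b.i).

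**Which events count.** The protocol (Safety/Adverse Event Monitoring) counts an event "whether or not it is considered related to the product/intervention". Its Analytic Plan for Aim 1 summarises AE incidence by system organ class, severity and relationship, with no frequency cut-off. SAP IV.b.i defines AEs as those with a potential association with INI and adds: "Adverse events for this study will consider: outcomes for which ≥5% experienced". The next sentence reads: "Adverse events will be characterized overall and stratified by treatment arm". Item 3 of the same list, the between-arm comparison, is "Number of adverse events comparing any INI versus placebo or HDINI versus LDINI versus placebo" and repeats no threshold.

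**Tolerability.** Protocol Aim 1 bases tolerability on the number and percentage who do not complete the study because of AEs. The visible SAP has no such analysis. The levels of its CONSORT diagram (VII) are "assessed for eligibility, randomized, treatment allocation, follow-up and analytic cohort", with no reasons for non-completion specified. Its drop-out analysis (IX.b.v) says: "Baseline covariates will be used to assess whether certain characteristics were associated with follow-up time".

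**The concern.** The protocol describes this as the first trial of intranasal insulin in MS, and safety is its stated primary question. On that question the two documents differ in rank, in which events count, and in whether tolerability is analysed. What is at stake is the between-arm AE analysis written in the SAP. An undefined frequency filter could remove a single serious event, or a cluster confined to one dose arm, depending on a denominator that nobody has fixed.

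**Working it through.** **1. The documents side by side**

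| Item | Protocol | SAP (section III onward) |
|---|---|---|
| Primary | Safety and tolerability | SDMT change |
| SDMT | Main secondary | Primary |
| AE scope | Related or not | Potential association with INI |
| Frequency limit | None | 5%, denominator not stated |
| Exemption for serious or grade 3+ | Not needed | None stated |
| Non-completion due to AEs | Number (%) | Not found |

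The first two rows conflict on any reading. The effect of the 5% row depends on what the sentence governs.

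**2. The plan's own figures**

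The protocol plans 35 per group, randomised 1:1:1, so 3 × 35 = 105, matching the design figure. Its SDMT power uses a 6-point difference, SD 9 and two-sided alpha 0.05: 6 / (9 × √(2/35)) = 2.79; 2.79 − 1.96 = 0.83; Φ(0.83) = 0.796, against a stated 80%. This reproduces. It confirms that the trial was sized on cognition; nothing below depends on it.

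**3. The 5% cut-off under each denominator**

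The cut-off is the smallest whole number at or above 0.05 × n.

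| Denominator | 0.05 × n | Cut-off | One participant | Five, all on 20 IU |
|---|---|---|---|---|
| Overall, 105 | 5.25 | 6 | 1.0%, dropped | 4.8%, dropped |
| Any INI, 70 | 3.5 | 4 | 1.4%, dropped | 7.1%, kept |
| One arm, 35 | 1.75 | 2 | 2.9%, dropped | 14.3%, kept |

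**4. How strong a signal could be lost on the overall denominator**

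The SAP names comparisons but no AE test in its visible text; exact tests are my choice. Splits are 20 IU / 10 IU / placebo.

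- 5/0/0, three-level: 3 × C(35,5) / C(105,5) = 3 × 324,632 / 96,560,646 = 0.010.
- 5/0/0, 20 IU versus placebo (5/35 against 0/35), Fisher two-sided: 0.054.
- 5/0/0, any INI versus placebo (5/70 against 0/35), Fisher two-sided: 0.17.
- 4/1/0, three-level: 0.12.

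**5. Chance that an event type is excluded**

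Assumed: true rate 10% on 20 IU and background rate b in each of the other two arms. With X ~ Bin(35, 0.10), Y ~ Bin(70, b) and Z ~ Bin(35, b):

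- overall rule: P(X + Y ≤ 5)
- any-INI rule: P(X + Z ≤ 3)
- at least 5% in any arm: P(X ≤ 1) × P(Z ≤ 1)²

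| b | Overall | Any INI | Any arm |
|---|---|---|---|
| 0% | 0.87 | 0.53 | 0.12 |
| 1% | 0.76 | 0.46 | 0.11 |
| 3% | 0.51 | 0.32 | 0.06 |
| 5% | 0.29 | 0.22 | 0.03 |

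**6. Scope**

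Steps 3 to 5 apply to the whole AE outcome only if the 5% sentence governs all of IV.b.i. If it governs only the item 1 summary, they describe what that summary omits, and the item 3 count is intact.

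**The case against.** A display-only reading of the 5% sentence is live. A 5% threshold is ordinary for a table of common events, the sentence does not say that only such events count, and item 3 has no threshold. As it reads, the sentence also has an unmatched closing bracket after it and no subject for its verb, so words, possibly the denominator, may have been lost in the text conversion. This stands: the scope is uncertain, and the harm from the threshold is conditional. Against it, the sentence sits beside the AE definition, speaks for the study as a whole, and is nowhere labelled a display rule.

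The protocol sizes the trial on cognition, so SDMT as the SAP's primary outcome has a rationale. The SAP before section III was not available and could explain the change. That tempers criticism of the choice but does not make the documents agree.

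The size rests on a worst case. The 5/0/0 split is the most extreme possible, the SAP's main contrast (any INI versus placebo) gives only p = 0.17 for it, and every rate in step 5 is assumed. This also stands.

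Three stronger readings are tempting and are not supported:

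- A reader might infer that rare or serious events will go unrecorded or unreviewed. The protocol still requires collection and grading of all AEs, real-time safety analysis, DSMB meetings for grade 3 or higher events, and serious AE reporting.
- A reader might infer that tolerability analysis has been abandoned. Protocol Aim 1 still specifies it, and nothing visible says the SAP replaces the protocol's plan. The SAP also leaves out the Aim 3 biomarkers, so it is not a full restatement.
- A reader might infer an unexplained switch of primary outcome. With part of the SAP unseen, only the mismatch itself can be stated.

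**Conclusion.** The primary/secondary mismatch is unconditional and must be reconciled. The narrower AE definition is also plain in the text.

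The 5% rule and the missing tolerability count should be fixed. Confidence on the rule's scope is moderate. If it governs the AE outcome, an event type seen in one participant is dropped on any denominator, and the cut-off is 6/105, 4/70 or 2/35 depending on a choice the plan does not make. Five events confined to 20 IU are then kept or lost by that choice alone. If it governs only a display, the effect is limited to what the display shows.

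The figures assume the planned 35 per arm; the 10% rate and the 0% to 5% backgrounds are illustrations, not forecasts.

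**What to change.** In the SAP:

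1. Replace the AE definition tied to a potential INI association with the protocol's definition, and include all AEs in the between-arm analysis.
2. Keep 5% only as a display threshold for a common-AE table, with its denominator stated (for example, at least 5% of participants in any arm). Do not apply it to serious AEs, grade 3 or higher AEs, or AEs leading to discontinuation.
3. Carry over the protocol's tolerability measure: number (%) per arm who failed to complete because of AEs.
4. Reconcile the primary objective and primary outcome so that the two documents agree, with a reason for whichever ranking is kept.

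The cost is SAP wording and longer AE tables. No new data are needed, because the protocol already collects all AEs.
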